results in cellular energetic impairment that diminishes ATP production and decreases sarcoplasmic reticulum Ca^{2+} -ATPase.²³ This results in decreased actin-myosin cross-bridge detachment, which is reflected in increased diastolic stiffness and decreased ventricular compliance. In addition, increased free radical production in HFpEF can result in damage to mitochondria and nuclei.²⁴ We will examine the bioenergetics of ubiquinol and/or D-ribose in patients with HFpEF both behaviorally (health status per KCCQ and Vigor scale) and biologically (6-minute walk test, echocardiographic imaging, lactate/ATP ratio, and BNP measurements). With emphasis on patient-centered care, it is important to assess patient perception of changes in health status and level of vigor as ubiquinol and/or D-ribose is administered. To our knowledge, the effects of combining ubiquinol and D-ribose in HFpEF patients have not been published and thus are innovative because of their synergistic potential.

B.2. Patient-centered Perspective. Since HFpEF is related to changes in cellular bioenergetics, it is important to evaluate behavioral measures of energy such as the Vigor scale as well as biological clinical outcomes. After meeting with 30 HFpEF patients and 10 caregivers, we found they were extremely interested in the question of whether ubiquinol, D-ribose, or both could improve their health status (i.e., reduce their shortness of breath, increase their ability to perform daily activities, etc.) and their energy levels. With the advanced speckle tracking echocardiogram images, lactate/ATP ratio, and BNP measurements, we can answer that question. Our data will help us compare the effectiveness of ubiquinol and D-ribose with usual treatment in this patient population.

B.3. Potential Impact of Racial/Ethnic and Cultural Differences. Studies raised concerns that the incidence of HF might vary among different racial/ethnic groups.^{25, 26} Thus, in this study we will oversample minorities as reviewers suggested, which will enable us to examine the relationship between HFpEF and racial/ethnic differences. Most of the data regarding treatments for HFpEF are derived from White populations,²⁷ and therefore it is important to include other racial/ethnic groups and examine whether the effects of ubiquinol and/or D-ribose follow similar patterns to those among whites.

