| Groups and Number of Subjects (69 per group/Total = 276 subjects). The power analyses require 62 subjects/group, but there will be 69 subjects/group based on the expected 10% attrition. | |
| 1. Control Group (Usual Care) N ₁ = 69 subjects: Receive no ubiquinol and no D-ribose; placebo capsules and powder per day. | 2. Ubiquinol Group N ₂ = 69 subjects: Receive 600 mg of ubiquinol per day; D-ribose placebo powder per day. |
| 3. D-ribose Group N ₃ = 69 subjects: Receive 15 g of D-ribose per day; placebo capsules for ubiquinol per day. | 4. Ubiquinol + D-ribose Group N ₄ = 69 subjects: Receive 600 mg ubiquinol and 15 g of D-ribose per day. |

Power and Statistical Analyses. Our power computations described below suggest including 62 subjects in each of the four study groups (ubiquinol, D-ribose, ubiquinol + D-ribose, and placebo). Since we expect about a 10% attrition rate, we will include 69 subjects in each group for a total of 276 subjects who will be randomized to one of the four groups. Efforts will be made to recruit 50% females. As suggested by the reviewers, we will oversample minority populations to increase the generalizability of data for minority groups (30% Black/AA, 30% Hispanic/Latino, 30% White, and 10% Other). In each group there will be Black/AA = 21, Hispanic/Latino = 21, White = 21, American Indian/Alaska Native, Asian, Native Hawaiian/Pacific Islander = 6 (Total = 69). A 10% attrition rate is anticipated since this is the approximate rate [name] (Co-PI) has experienced with her heart failure clinical trials at the same locations. Reasons for the subject's attrition were that they did not want to continue in the study, change in geographic location, or illnesses.

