Statistical Analysis of Effect of Treatment Duration. The effect of ubiquinol treatment duration on KCCQ Clinical Summary changes will be further investigated by fitting a random intercept linear model that will use the repeated measures provided by the subjects. Each subject will contribute to the model if any of the following two measures of the dependent variable are available: (1) a change in KCCQ score from baseline to the end of the 6th week, and (2) a change from baseline to the end of the 12th week. One dummy variable indicating whether the change corresponds to a treatment duration of 6 weeks (dummy=0) or 12 weeks (dummy=1) will be included as an independent variable as well as an indicator of ubiquinol treatment, gender, and race/ethnicity. This analysis will include subjects with complete or incomplete data. A positive and significant regression coefficient for the treatment duration dummy will signal that 6 weeks are not sufficient to obtain a change in KCCQ score equivalent to the change obtained after 12 weeks of treatment. Further, a significant regression coefficient for the ubiquinol treatment indicator will provide additional evidence of differences in KCCQ score changes between ubiquinol and placebo groups. To explore whether there is heterogeneity of ubiquinol effects across subjects, an additional random effects linear model will treat the regression coefficient of the ubiquinol indicator as a random coefficient. Analogous analyses will be made with the other continuous variables: POMS Vigor scale, E/e' ratio, PAP, and BNP and with D-ribose in place of ubiquinol. Random effects linear models use the information provided by participants with incomplete data such as participants discontinuing treatment. These models are robust to the presence of missing values under a missing-at-random assumption. To explore the sensitivity of the models to the presence of possible non-ignorable missing data, such as missing data caused by informative drop-out, a joint random intercept linear model will be fitted that will simultaneously model the KCCQ score and the missingness process.⁸⁹

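### The supporting random-intercept model reads its ubiquinol coefficient as ubiquinol versus placebo, but with four arms and no product term it also contains half the ubiquinol-by-D-ribose interaction

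*Combined protocol and SAP*

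**What the plan says.** The model is in C.5, Statistical Analysis of Effect of Treatment Duration. The outcome is the change in KCCQ Clinical Summary score, from baseline to week 6 and from baseline to week 12. A dummy for duration "will be included as an independent variable as well as an indicator of ubiquinol treatment, gender, and race/ethnicity". Neither a D-ribose indicator nor a ubiquinol-by-D-ribose product is listed.

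On who enters, the text says "Each subject will contribute to the model if any of the following two measures of the dependent variable are available", and it excludes no arm. On interpretation, it says that "a significant regression coefficient for the ubiquinol treatment indicator will provide additional evidence of differences in KCCQ score changes between ubiquinol and placebo groups". The analysis is repeated for POMS Vigor, E/e', PAP and BNP, and "with D-ribose in place of ubiquinol", so the two supplements are never in the same model.

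Three other places bear on this:

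- C.5, Hypotheses #1 and #2, compares arms in pairs with t-tests, Bonferroni-corrected for four comparisons.
- C.5, Statistical Analyses of Interaction, fits both indicators and their product to the week-12 change, adjusted for gender and race/ethnicity. The duration section does not refer to it.
- C.2 and C.3 (Hypothesis #2) schedule the KCCQ and the Vigor scale at baseline and 12 weeks only.

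**The concern.** Ubiquinol is taken in two of the four arms: alone, and with D-ribose. A single ubiquinol indicator fitted to all four arms therefore does not isolate the ubiquinol-alone arm against the placebo arm. Whatever is special about the combination enters the coefficient.

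A zero interaction cannot be taken for granted here. B.1 says that the effects of combining the two supplements in HFpEF "have not been published and thus are innovative because of their synergistic potential", and C.5 plans a test of the interaction. The KCCQ pilot (Table 1) had no D-ribose-alone group, so it cannot estimate one.

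At stake is a report in which the corrected ubiquinol-versus-placebo t-test is null while this model is presented as further support for the same comparison. The opposite error is also possible. If the combination does no better than either supplement alone, the model understates a real ubiquinol effect.

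**Working it through.** **Inputs from the plan (C.5).** Four equal arms, 62 per arm after attrition; a 10-point difference; SD of change 12.3; two-sided 0.05, or 0.0125 after Bonferroni for four comparisons.

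**Step 1. Reproduce the plan's power.** The noncentrality is (10/12.3) × √(62/2) = 4.53. The two-sided 0.0125 critical value is 2.50. Power is Φ(4.53 − 2.50) = Φ(2.03) = 97.9% (97.6% with the noncentral t), against the stated 98%. Attrition: 62/0.90 = 68.9, so 69 per arm. The inputs are understood as the plan uses them.

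**Step 2. What the coefficient estimates.** Let P, U, D and UD be the true mean changes in the four arms. With equal arms and a ubiquinol indicator only:

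coefficient = (U + UD)/2 − (P + D)/2 = (U − P) + ½ × (UD − U − D + P).

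The last bracket is the interaction. The D-ribose model has the same form with U and D exchanged.

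**Step 3. Scenarios (KCCQ points).**

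| P / U / D / UD | U − P | Interaction | Coefficient |
|---|---|---|---|
| 0 / 0 / 0 / 10 (combination only) | 0 | 10 | 5 |
| 0 / 10 / 10 / 10 (ceiling) | 10 | −10 | 5 |
| 0 / 10 / 0 / 20 | 10 | 10 | 15 |
| 0 / 10 / 10 / 20 (additive) | 10 | 0 | 10 |
| 0 / 0 / 10 / 10 (D-ribose only) | 0 | 0 | 0 |

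The last two rows show that leaving out the D-ribose main effect does no harm when the interaction is zero. In the first row the D-ribose model also gives 5, so one combination effect appears under each supplement.

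**Step 4. How often the coefficient is significant, combination-only case, one week-12 change per patient.** In the ubiquinol half, the two arm means differ by 10, which adds variance 25 there and 0 in the other half, 12.5 on average. The residual SD is √(12.3² + 12.5) = 12.8. The SE is 12.8 × √(2/124) = 1.63, and 5/1.63 = 3.08. Power is Φ(3.08 − 1.96) = 87% at 0.05 and Φ(3.08 − 2.50) = 72% at 0.0125.

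A simulation of 20,000 trials with the same inputs, without the demographic covariates, gives:

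| Model | Mean coefficient | Significant at 0.05 | At 0.0125 |
|---|---|---|---|
| As written, four arms | 5.0 | 87.6% | 72.3% |
| Plus D-ribose main effect only | 5.0 | 88.4% | 73.9% |
| Plus D-ribose and product | 0.0 | 4.8% | 1.2% |
| Ubiquinol-alone and placebo arms only | 0.0 | 4.9% | 1.3% |

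With no effect in any arm, the model as written rejects in 4.9% of trials at 0.05. It is a sound test of the pooled contrast; only the label is wrong. For a 5-point combination-only effect the coefficient averages 2.5, and about 36% of trials are significant at 0.05 (4,000 simulated trials).

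**Step 5. If week-6 changes existed.** Assume the same effect at week 6 and a correlation of 0.3 to 0.9 between the two changes (the documents give none). The combination-only rates become 96% to 88% at 0.05 and 89% to 74% at 0.0125.

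**The case against.** **Only two arms may have been meant.** The sentence on who contributes is a missing-data rule, not a list of arms. The stated comparison is between ubiquinol and placebo groups, and Hypothesis #6 uses similar words for a two-arm t-test. Under that reading the coefficient is correct. This reading is possible but nowhere written. The preceding section uses the same kind of ubiquinol indicator across all four arms, which makes the four-arm reading the natural one. On either reading the plan needs a sentence.

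**The main analyses already separate the arms.** This stands. In the combination-only case, the ubiquinol-versus-placebo t-test keeps its 1.25% error rate. The combination-versus-ubiquinol test has about 98% power. The interaction test (SE 12.3 × √(4/62) = 3.12) has about 89% power at 0.05. For KCCQ, a misleading coefficient would therefore usually be contradicted by better analyses. The protection is weaker for a 5-point effect, where the interaction test has about 36% power, and for BNP, which the interaction section does not name.

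**It is not a bare repeat of the t-test.** As written, the model also uses week-6 changes and patients without week 12. That stands: the two analyses overlap but are not identical.

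**What a reader might infer but should not.** One might conclude that the whole combination effect is credited to ubiquinol; half of it is. One might blame the missing D-ribose main effect; with balanced arms that omission causes no bias, and restoring it alone leaves the coefficient at 5. One might call synergy a trial hypothesis; none of Hypotheses #1 to #6 states it, and C.5 offers it as an opportunity to examine.

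**Conclusion.** The concern holds for this supporting model. Fitted to four equal arms, its ubiquinol coefficient is ubiquinol versus placebo plus half the interaction, and it supports the plan's reading only if the interaction is zero. A combination-only effect of 10 points would appear as 5 points for ubiquinol and, in the other model, 5 points for D-ribose. Each would be significant in about 87–88% of trials at 0.05 and about 72% at 0.0125. Under a ceiling, a true 10-point ubiquinol effect would appear as 5.

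These figures assume that all four arms enter, 62 per arm, SD 12.3 and one week-12 change per patient. The formula needs only the balanced arms. The documents do not support extending the point to the trial's principal conclusions, because the pairwise t-tests and the interaction regressions are unaffected.

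A separate inconsistency limits the model more basically. No KCCQ is scheduled at week 6, so the 6-week change it requires is not collected. With one change per patient, the duration dummy is constant and the random intercept cannot be separated from residual error. The ubiquinol coefficient keeps its pooled meaning.

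**What to change.** 1. In the duration section, add the D-ribose indicator and the product term, as the interaction section already does. Read the ubiquinol coefficient with D-ribose at 0, and the D-ribose coefficient with ubiquinol at 0. Apply this to KCCQ, Vigor, E/e', PAP and BNP. Adding the D-ribose indicator without the product is not enough.
2. If only two arms were intended, say so instead: ubiquinol-alone and placebo in one model, D-ribose-alone and placebo in the other.
3. Describe the result as a supportive analysis that overlaps the pairwise t-test, not as independent evidence.
4. Reconcile the 6-week change with the visit schedule in C.2 and C.3. If no week-6 measurement exists, the corrected model reduces to the interaction regression and can be dropped or cross-referred.

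Items 1 to 3 change wording and analysis code only; they need no new patients or data. The price is precision: the standard error rises from about 1.6 points to 12.3 × √(2/62) = 2.2. That is the correct precision for the comparison that the plan names.

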Initially, potential subjects from HERON, Pioneers, and KUH outpatient HF clinics will be interviewed by phone for potential recruitment in the study. Two nurse practitioners and a cardiologist on our research team work in the outpatient HF clinics and will refer patients to us. Patients will be required to speak English, and the informed consent and patient information will be written at the 8th grade level. We will collaborate with our Human Subject Protection Program to ensure our consent form complies with the US Department of Health and Human Services (HHS) federal guidelines and obtain informed consent from eligible patients (Appendix 10). Patients that have consented will be provided a 1-week supply of placebo ubiquinol pills (instructed to take 2 pills/day) and placebo D-ribose powder (instructed to take 3 scoops/day) as a pre-randomization run-in period to evaluate compliance to the supplements. Patients will be scheduled for an appointment at the CTSU in 1 week following the run-in period. Patients that demonstrate an 80% compliance rate of ubiquinol intake (as evidenced by pill count) and an 80% compliance rate of D-ribose powder intake (as evidenced by weight of the containers) will be eligible to be randomized into a group assignment. The enrolled patients with 80% compliance will then be randomized into four groups (69 subjects in each group) to receive ubiquinol (600 mg daily), D-ribose (15 g daily), ubiquinol plus D-ribose, or placebo for a period lasting 12 weeks. Both the ubiquinol and the D-ribose supplements used in the study will have a certificate of analysis from the manufacturer (Appendix 9). The Project Director will receive the identified list of recruited subjects from the Principal Investigator (PI) and will randomly assign subjects to one of the groups using a list created by a computer-based random number generator. All supplements and the placebo will be indistinguishable in packaging and will be distributed by the Project Director independent of the PI so that the allocation of subjects to a treatment or placebo group will be concealed from both subjects and research personnel.

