The regional HF statistics indicate are: 10% Black/African Americans (AA), 13% Hispanic/Latino, 76% White, and 1% Asian, Native American/Alaskan Native, Native Hawaiian/Pacific Islander. The racial and ethnic population distribution planned coincides with these national and regional figures. The Kansas City Metropolitan Statistical Area confirms these percentages in the general population.⁹⁹ In this study, we will oversample minorities (reviewer's suggestion), which will enable us to examine the relationship between HFpEF and racial/ethnic differences. Most of the data regarding treatments for HFpEF are derived from white populations,²⁷ and therefore it is important to include other racial/ethnic groups and examine whether the effects of ubiquinol and/or D-ribose follow similar patterns to those among whites. For this study, a total of 276 subjects will be randomized to one of the four groups. As suggested by the reviewers, we will oversample minority populations to increase the generalizability of data for minority groups (30% Black/AA, 30% Hispanic/Latino, 30% White, and 10% Other). Each group will be Black/AA = 21, Hispanic/Latino = 21, White = 21, American Indian/Alaska Native, Asian, Native Hawaiian/Pacific Islander = 6 (Total = 69). The University of Kansas Medical Center (KUMC) Healthcare Enterprise Repository for Ontological Narration (HERON) database, Pioneers Recruitment Registry (Pioneers), and chronic HF clinic at the University of Kansas Hospital (KUH) will be used to recruit subjects. These registries provide clinical/translational investigators with the numbers of patients at KUH who meet the inclusion criteria for clinical trials and contact information for patients who sign up with KUMC's Frontiers participant registry. Based on the HERON, there will be approximately 7,100 subjects with HFpEF available to be screened for enrollment in this study. The Swope Health Services in Kansas City, Missouri has a large Black/AA and Hispanic/Latino population. The Pioneers Registry has a relationship with Swope Health Services and can assist us with electronic informed consent forms, email verification, and subject recruitment at this site.

Inclusion of Children.

All subjects will be 50 years or over, as HFpEF is more prevalent in older adults. Children (the age to 18 years and younger) will not be included in this study because diastolic heart failure is very rare in the pediatric population.

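### A random coefficient on the between-patient ubiquinol indicator compares arm variances; it cannot identify or quantify how much the effect varies between patients

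*Combined protocol and SAP*

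**What the plan says.** Section C.5, under Statistical Analysis of Effect of Treatment Duration, studies KCCQ Clinical Summary changes by "fitting a random intercept linear model that will use the repeated measures provided by the subjects". A dummy for treatment duration "will be included as an independent variable as well as an indicator of ubiquinol treatment, gender, and race/ethnicity". No D-ribose term is listed, and the text does not say which of the four arms enter.

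A further model follows. Its purpose is stated as "To explore whether there is heterogeneity of ubiquinol effects across subjects", and it "will treat the regression coefficient of the ubiquinol indicator as a random coefficient". Analogous analyses are planned for Vigor, E/e', PAP and BNP, and for D-ribose in place of ubiquinol. No covariance structure, test or rule of interpretation is given for the variance component.

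Section C.2 randomises each patient once, to one of four parallel groups of 69, for 12 weeks.

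Sections B.3 and Inclusion of Women and Minorities say that oversampling will let the study "examine whether the effects of ubiquinol and/or D-ribose follow similar patterns to those among whites". In the C.5 regressions (interaction and treatment duration) race/ethnicity enters only as a main effect. The only interaction specified is ubiquinol by D-ribose.

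**The concern.** A random coefficient measures how an effect varies between patients when each patient is seen at more than one level of the covariate. Here nobody is seen both on and off ubiquinol. The fitted variance component therefore cannot be read as the spread of individual ubiquinol effects. A value near zero could be taken to mean that ubiquinol works alike in everyone, and a large value to mean that patients respond differently, when the data establish neither.

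The plan also has no other analysis of whether the effect differs between patients. The racial/ethnic question, which is a stated reason for the 30/30/30/10 recruitment, is left without a model that can answer it, because a main effect of race/ethnicity says nothing about differences in treatment effect.

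**Working it through.** **Inputs from the documents.** Parallel allocation, 69 per arm and 62 evaluable (C.2, C.5). SD of KCCQ change 12.3 and important difference 10 points (C.5, Hypotheses #1 and #2). Pilot changes 16.3 ± 7.0 and 30.0 ± 13.2, n = 5 each (C.4, Table 1). D-ribose increment 13.7 points (C.5). Per arm 21 Black/AA and 21 White patients (C.5).

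**The plan's SD.** The plan gives no figure for this model, so its SD is checked first.
- Combined: sqrt[(4×7.0² + 4×13.2² + 10×6.85²)/9] = sqrt(1362.2/9) = 12.30, which reproduces 12.3.
- Pooled within group: sqrt[(7.0² + 13.2²)/2] = sqrt(111.62) = 10.57.

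All ten pilot patients were treated. The documents give no KCCQ SD for untreated patients, so its use for them below is an assumption.

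**What the data identify.** Let patient i have untreated level b0 (variance s0²) and individual effect b1 (variance s1²), with covariance s01.
- Off ubiquinol: between-patient variance = s0².
- On ubiquinol: between-patient variance = s0² + 2·s01 + s1².

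The difference, s1² + 2·s01, is one quantity with two unknowns. A second change score per patient would separate s0² from residual error but would not split s1² from s01, because the indicator is still constant within the patient.

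**Likelihood check.** Assumptions: total SD 12.3 and between-patient share of variance 0.6, so s0² = 0.6 × 151.29 = 90.8. On one simulated data set (62 per arm), effect SDs of 0, 8 and 16 with s01 of 0, -32 and -128 all give s1² + 2·s01 = 0 and the same log-likelihood, -926.1138. Equal arm variances fit any effect SD from 0 to 2·s0 = 2 × 9.53 = 19.1 points. That upper limit is 13.5 to 22.0 for shares of 0.3 to 0.8. The plan's important mean difference is 10 points.

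**Illustration (all inputs assumed).** Effect SD 6; treated SD = sqrt(SD0² + 6² + 2·r·SD0·6), where SD0 is the untreated SD and r the correlation between a patient's untreated change and individual effect.

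| r | SD0 = 12.3 | SD0 = 10.57 |
|---|---|---|
| -0.5 | 10.65 | 9.18 |
| -0.25 | 12.26 | 10.77 |
| 0 | 13.69 | 12.15 |
| +0.25 | 14.97 | 13.39 |

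The same heterogeneity appears as less, about equal or more variance on ubiquinol. Exact cancellation at SD0 = 12.3 needs r = -6/(2×12.3) = -0.244.

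**How a test behaves.** Simulated 5% boundary likelihood-ratio test with covariance fixed at zero, two changes per patient, 62 per arm and share 0.6 (4,000 runs per setting):
- effect SD 8, s01 = -32: rejects about 5%, its size;
- effect SD 8, s01 = -60: about 0%;
- effect SD 8, s01 = 0: about 50% (44% to 63% over shares 0.8 to 0.3), or 39% with one change per patient.

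**Omitted D-ribose term.** Suppose each side of the ubiquinol indicator pools two arms, and D-ribose adds 13.7 points only when given with ubiquinol. The ubiquinol side gains 13.7²/4 = 46.9 points². The test then rejects 58% of the time (49% to 72% over the same shares), or 45% with one change per patient, although all patients within an arm have identical effects. If D-ribose adds 13.7 points on both sides, rejection is about 4%.

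**Schedule.** The model uses "a change in KCCQ score from baseline to the end of the 6th week", but C.2 schedules the KCCQ at baseline and 12 weeks only, and Participation of Human Subjects 1.1 describes two visits. With one change per patient the random intercept cannot be separated from residual error, and the model reduces to unequal total variances.

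**The case against.** A reader might infer that the model can show nothing about heterogeneity. The documents do not support that. Under randomisation a constant additive effect implies equal variances, so a real variance difference is one-way evidence against a constant effect. The 50% rejection rate at effect SD 8 and zero covariance shows that the model is not blind.

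A reader might also infer that the trial will report variance differences as differing response. The plan offers the model as exploratory and additional, with no test or threshold attached, so that would be a forecast about reporting.

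Nor does near-cancellation force a zero estimate. With true SDs of 12.26 and 12.30 and 62 per arm, the treated sample variance is the larger about 49% of the time, and the fitted component is then positive if the covariance is fixed at zero.

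The illustration rests on an effect SD and correlations that no document gives, and the D-ribose mechanism needs pooled arms and a ubiquinol-by-D-ribose interaction. The racial/ethnic gap is a separate omission that would remain if the random-coefficient model were removed.

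These points limit the claim. They do not change the algebra: the variance component is still not the SD of individual effects.

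**Conclusion.** The point holds as a statement about what the model estimates. In this design it can test only whether between-patient variance differs by arm. It cannot identify or quantify the SD of individual effects, and a null result does not show uniformity. This follows from the allocation alone, and week-6 data would not change it.

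The sizes depend on assumptions: an untreated SD borrowed from treated pilot patients, a between-patient share of 0.3 to 0.8, and the stated covariances. A variance difference has an alternative explanation in the missing D-ribose term only if arms are pooled and D-ribose acts differently with and without ubiquinol.

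The effect on the trial is limited. The primary t-tests and the sample size do not use this model. It is still worth correcting, because the plan's only analysis of variation between patients does not estimate what it is meant to explore, and the racial/ethnic aim has no matching analysis.

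**What to change.** 1. Drop the random-coefficient model as a measure of heterogeneity. Alternatively, keep it as an exploratory comparison of arm variances: state the covariance assumption, say which arms enter, and include D-ribose and its interaction with ubiquinol. Apply the same to the other outcomes and to the D-ribose version.
2. In the regression under Statistical Analyses of Interaction, prespecify treatment-by-race/ethnicity, treatment-by-sex and treatment-by-baseline-KCCQ interactions (adding baseline KCCQ as a main effect). Report effects with confidence intervals and call them exploratory. The first of these serves the aim in B.3 and Inclusion of Women and Minorities.
3. Reconcile the week-6 change with the visit schedule if any repeated-measures model is kept.

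The cost is plan wording and a few model terms on data already to be collected. The drawback is precision. For a Black-versus-White difference in the ubiquinol-versus-placebo effect, with 21 patients in each of four cells and SD 12.3 assumed, the 95% half-width is 1.96 × 12.3 × sqrt(4/21) = 10.5 points before attrition; with SD 10.57 it is 9.0. Either is close to the 10-point difference that the plan calls important, so such estimates can describe but will rarely settle the question.
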